#### 13.1.2 Serious Adverse Events

A Serious Adverse Event (SAE) is any untoward medical occurrence (whether considered to be related to investigational product or not) that at any dose:

- Is fatal.
- Is life-threatening (places the subject at immediate risk of death)
- Requires inpatient hospitalization or prolongation of existing hospitalization.
- Is a persistent or significant disability/incapacity, or
- Is a congenital abnormality/birth defect.

A hospitalization meeting the regulatory requirement for the "serious" criteria is any inpatient hospital admission that includes a minimum of an overnight stay in a health care facility.

Any event that does not exactly meet this definition yet, in the investigator's opinion represents a significant hazard can be assigned the "other significant hazard" regulatory reporting serious criteria.

Additionally, important medical events that may not be immediately life threatening or result in death or hospitalization but that may jeopardize the subject or require intervention to prevent one of the outcomes listed above, or result in urgent investigation, may be considered serious. Examples include allergic bronchospasm, convulsions, and blood dyscrasias.

SAEs will be collected and reported throughout the study duration beginning with enrollment through the end of the Long-Term Follow-Up period. If early termination of study treatment occurs, SAEs will continue to be collected until the event resolves.

## 13.2 Reporting Procedures

All adverse events occurring after FCX-007 administration observed by the investigator or reported by the subject (whether or not attributed to investigational product), will be reported on the case report form.

Medically significant adverse events considered related to the investigational product by the investigator or the sponsor will be followed until resolved or considered stable. The investigator must assign the following attributes: description; dates of onset and resolution; severity; assessment of relatedness to investigational product, and action taken. The investigator may be asked to provide follow-up information.

All deaths occurring on study must be reported to Fibrocell. These include deaths during the Long-Term Follow-Up period. For all deaths, available autopsy reports and relevant medical reports should be provided to the Medical Monitor.

The investigator should notify the IRB of serious adverse events occurring at the site and other

CONFIDENTIAL Page 56 of 75

Fibrocell Technologies RDEB Phase I/II Protocol

Final Version 8.0, 29 Oct 2019

adverse event reports received from Fibrocell, in accordance with local procedures.

It will be left to the investigator's clinical judgment whether or not an adverse event is of sufficient severity to require the subject's removal from study. A subject may also voluntarily withdraw from study due to what he or she perceives as an intolerable adverse event. If either of these occurs, the subject will be asked to undergo an early termination assessment and be given appropriate care under medical supervision until symptoms cease or the condition becomes stable. If the subject was permanently withdrawn from the study due to a serious adverse event, this information must be included in either the initial or follow-up Serious Adverse Event Report Form, and in the End of Study Case Report Form.

The severity of toxicities will be assessed on the following scale with appropriate clinical definitions: Grade1 = mild adverse event, Grade2 = moderate adverse event, Grade3 = severe adverse event, Grade4 = immediate life threatening adverse event, and Grade5 = fatal adverse event.

The relationship of adverse events to the investigational product will be assessed by the investigator using good clinical judgment according to the following definitions:

- Unrelated: no temporal association or the cause of the event has been identified, or the study drug cannot be implicated based upon available information.
- Unlikely (related): a potential relationship between study drug and the event could exist (i.e., the possibility cannot be excluded), but the event is most likely explained by causes other than the study drug.
- Possible/Possibly (related): temporal association, but other etiologies are likely to be the
  cause. However, involvement of the study drug cannot be excluded based upon available
  information.
- Probable/Probably (related): the event and use of study drug are temporally related, and the event is more likely explained by study drug than by other causes.
- Definite/Definitely (related): established temporal or other association (e.g., re-challenge) and
  event is not reasonably explained by the subject's known clinical state or any other factor,
  based on available information.

#### 13.2.1 Post-FCX-007 Administration Adverse Event Monitoring

The Investigator must monitor the subject's wounds closely for additional blister formation and expansion of the border of the wound during injections and immediately post-administration up to the 2 day follow up visit. Additional blister formation and/or expansion of the border of the wound must be recorded as an adverse event.

CONFIDENTIAL Page 57 of 75

Fibrocell Technologies RDEB Phase I/II Protocol Final Version 8.0, 29 Oct 2019

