# 7.2 Wound Monitoring Period

The Wound Monitoring Period may consist of 2 or more visits during the 4-month period in which FCX-007 is being manufactured. The purpose of the visits is to image potential target wounds. Potential target wounds will also undergo a skin examination during these visits. The overall length of the Wound Monitoring Period may vary due to manufacturing or data analysis. The first visit may be scheduled at least 30 days after the Screening visit and subsequent visits may be scheduled at least 30 days apart. If possible, the last wound monitoring visit may occur no more than 60 days prior to the injection of FCX-007.

Because the length of the manufacturing period may vary, the wound monitoring visits should be based on the best available estimates of when the first injection will be available.

If insufficient cell growth occurs and FCX-007 cannot be manufactured, subjects will be asked for additional manufacturing biopsies.

Collection of blood for RCL analysis can be obtained at a wound monitoring visit if not taken at screening. Results must be available prior to Day 0.

Manufacturing biopsies can be taken at Wound Monitoring Visit 1 if not obtained at the Screening Visit.

CONFIDENTIAL Page 30 of 75

Final Version 8.0, 29 Oct 2019

# 7.3 Visits 2 through 10

Study procedures are scheduled at Visits 2 (Day -2), 3 (Day 0), 4 (Day 2), 5 (Week 4), 6 (Week 12), 7 (Week 16), 8 (Week 25), 9 (Week 32), and 10 (Week 52). The Investigator may extend the subject's stay for any visit at his/her discretion based on any adverse events experienced.

Unscheduled procedures may occur during this period and resulting data should be captured on Unscheduled Visit case report forms. If deemed necessary, Investigators may attend to the subject at the hotel to check on their progress. Nursing support for bandage changes will be provided as needed.

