### 7.3.2 Visit 3 (Day 0; Day of Injection)

Visit 3 procedures are scheduled to occur on the day of receipt of FCX-007. The following procedures will be performed during this visit:

- Re-evaluation of inclusion/exclusion criteria
- Review of medical and medication history
- Physical and Skin Exam
- Vital signs: blood pressure, heart rate, respiratory rate, temperature
- Bacterial culturing of target wounds (may be done if clinical evaluation is

CONFIDENTIAL Page 31 of 75

indicative of infection)

- Surgical marking around the target wounds and on the intact skin
- Digital imaging of injection sites
- Tattoos will be placed on non-blistered skin near the target wounds for the purpose of calibrating the post-dose imaging.
- Tattoos will also be placed next to the intact skin injection sites for the purpose of precisely locating the biopsy sites at follow-up visits.
- Randomly assign each wound of a target wound pair to either active treatment or control (Visit 3 only).
- Biopsy collection to be used as IF/DIF and IEM.
  - Biopsy location markings must be imaged prior to collection.
  - Biopsy collection must occur prior to administration
- FCX-007 administration to target wounds
- FCX-007 administration to the intact skin.
- Post-dose digital imaging
- Post-dose assessment of concomitant medications and adverse events

As noted above, the subject may remain at the Investigative Site or in a nearby hotel for up to 2 days following FCX-007 administration. During this period, the subject will be monitored for autoimmune reactions to FCX-007. At a minimum, subjects will be contacted once per day on days in which there are no scheduled procedures.

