### 7.3.3 Visit 4 (Day 2)

Visit 4 procedures are scheduled to occur up to 2 days (±1 day) after Visit 3. The following procedures will be performed during this visit:

- Assessment of adverse events
- Assessment of concomitant medications
- Skin Exam
- Vital signs: blood pressure, heart rate, respiratory rate, temperature
- Digital imaging of wounds

Following Visit 4, the subject may return home.

CONFIDENTIAL Page 32 of 75

Final Version 8.0, 29 Oct 2019

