### 7.3.4 Visit 5 (Week 4)

The visit window for the Week 4 visit is ±2 days. The following procedures will be performed during this visit:

- Assessment of adverse events
- Assessment of concomitant medications
- Skin exam
- Vital signs: blood pressure, heart rate, respiratory rate, temperature
- Collection of blood (approximately 19 mL) for laboratory tests:
  - Serum chemistry
  - Hematology
  - Analysis for C7 antibodies
  - RCL analysis
- Digital imaging of wounds
- Investigator Assessment of Wound Healing.
- Bacterial culturing of target wounds (may be done if clinical evaluation is indicative of infection).
- Skin biopsies will be collected for IEM, genomic DNA/mRNA and/or IF/DIF evaluation at the site of Investigational Product/placebo administration as outlined in **Table 2**. Biopsy location markings must be imaged prior to collection.
- Skin biopsies will be collected from intact skin administration sites for IEM, genomic DNA/mRNA and/or IF/DIF evaluation as outlined in **Table 2**.
- Surgical marking around the target wounds and on the intact skin
- Tattoos will be placed on non-blistered skin near the target wounds for the purpose of calibrating the post-dose imaging.
- Tattoos will also be placed next to the intact skin injection sites for the purpose of precisely locating the biopsy sites at follow-up visits.
- FCX-007 administration to target wounds
- FCX-007 administration to the intact skin.
- Post-dose digital imaging
- Post-dose assessment of concomitant medications and adverse events

CONFIDENTIAL Page 33 of 75

Final Version 8.0, 29 Oct 2019

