#### A: Treatment of an Entire Wound

#### **B: Treatment of a Partial Wound**

#### 9.4.3 Visit 5 Administration

Target wounds are administered investigational product up to two times throughout the treatment period; once at Visit 3 (Day 0) and again at Visit 5 (Week 4).

CONFIDENTIAL Page 45 of 75

Final Version 8.0, 29 Oct 2019

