## 11 Procedures: Safety Assessments

Timing of safety assessments must be performed in accordance with **Table 2 - Schedule of Events**. Safety assessments include evaluation of medical and medication history, physical / skin examination, vital signs, AEs, and laboratory evaluations. AEs will be captured between visits through use of an Adverse Event Diary. Post-administration changes in these assessments that are deemed to be clinically significant by an Investigator or Sub-Investigator will be assessed as AEs.

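### After a Week 4 dose to target wounds, no visit or contact is scheduled until Week 12; the 2-day visit that ends the close wound watch follows the Day 0 dose only

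*Combined protocol and SAP*

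**What the plan says.** Section 13.2.1 carries a general heading on monitoring after FCX-007 administration. Its first sentence makes close wound monitoring mandatory during injections and "immediately post-administration up to the 2 day follow up visit". Its second sentence requires new blisters or border expansion to be recorded as an AE and sets no time or dose limit.

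The schedule contains one visit that fits that description. Section 7.3.3 states: "Visit 4 procedures are scheduled to occur up to 2 days (±1 day) after Visit 3". Visit 4 includes a skin examination, wound imaging and AE assessment. The optional stay of up to 2 days near the site, and the rule that "At a minimum, subjects will be contacted once per day on days in which there are no scheduled procedures", are both in section 7.3.2, under Visit 3. Table 2, footnote 4, likewise places the stay between Visits 2 and 4.

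Section 9.4.3 allows a second wound dose: "Target wounds are administered investigational product up to two times throughout the treatment period". Section 7.3.4 lists that dose at Visit 5 (Week 4), followed on the same day by imaging and by "Post-dose assessment of concomitant medications and adverse events". It lists no later contact. The next visit in section 7.3 and Table 2 is Visit 6 (Week 12).

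Between those visits, section 11 provides that "AEs will be captured between visits through use of an Adverse Event Diary". Section 7.3 adds that "The Investigator may extend the subject's stay for any visit at his/her discretion based on any adverse events experienced", that investigators may see subjects at the hotel if needed, and that "Nursing support for bandage changes will be provided as needed". Section 7.4 allows unscheduled procedures at the Investigator's discretion.

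**The concern.** Safety is the primary objective (section 2.2.1). Section 13.2.1 singles out new blisters and border expansion during and shortly after injection as effects the Investigator has to look for. The second wound dose is given by the same route, at the wound margin, so the same early effects are possible.

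With the plan followed exactly, a scheduled on-site look at the wounds takes place about 2 days after the first dose. After the second dose there is the dosing-day check and then no scheduled look or contact for about eight weeks. A short-lived expansion or a few new blisters on days 1 to 3 would be found only if the subject enters them in the diary, or if as-needed nursing or a discretionary visit brings them to light. By Week 12 such a change may have resolved, or may not be separable from the natural variation in wound area that section 3.1 acknowledges.

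The information at stake is useful. Week 4 is the only planned re-exposure of a treated wound, and section 13.2 gives re-challenge as an example of the association behind a definite causality rating. The section 11.1.2 review before Phase II takes data through Visit 5, so it need not include any follow-up beyond the day of a subject's second dose.

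**Working it through.** The plan states no figure for this gap. The check compares the schedule after each dose and then does the date arithmetic, counting weeks as 7 days from Day 0.

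**Scheduled follow-up after each wound dose**

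| | Day 0 dose (Visit 3) | Week 4 dose (Visit 5) |
|---|---|---|
| Same-day imaging and AE assessment | Yes (7.3.2) | Yes (7.3.4) |
| Skin examination and imaging about 2 days later | Yes, Visit 4 (7.3.3) | None |
| Daily contact on days without procedures | Yes (7.3.2), in a period described as monitoring for autoimmune reactions | None stated |
| Next scheduled visit | Visit 4 | Visit 6 (Week 12) |
| AE diary, as-needed nursing, unscheduled visits | Yes | Yes |

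The difference that bears on wounds is the Visit 4 skin examination and imaging. The daily contact is not described as a wound check, so it is not counted as a lost wound look.

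**Time from dose to next scheduled visit or contact**

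- Day 0 dose: Visit 4 is at 2 ± 1 days, so 1 to 3 days.
- Visit 5: 4 × 7 = day 28, window ±2 days, so day 26 to day 30.
- Visit 6: 12 × 7 = day 84, window ±1 week, so day 77 to day 91.
- Nominal gap: 84 − 28 = 56 days.
- Shortest gap: 77 − 30 = 47 days.
- Longest gap: 91 − 26 = 65 days.
- Scheduled visits or contacts inside the gap: 0.

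**Number affected (upper bounds)**

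- Subjects (section 3.3): 6 + 6 = 12, or 6 + 7 = 13 with the optional seventh Phase II subject. Each has at most one second administration to wounds.
- Treated wounds: up to three pairs per subject, one treated per pair, so at most 3 × 12 = 36, or 3 × 13 = 39.

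These are ceilings. Section 3.1 allows the second dose to go to intact skin alone, and the limit of about 54 linear cm on total injection length (section 9.1) means that not every subject will have three treated wounds.

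**After the proposed change**

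A contact 2 ± 1 days after the Week 4 wound dose brings the first scheduled follow-up from 56 days (47 to 65) to 2 days (1 to 3).

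**The case against.** The strongest reply is that 13.2.1 names a single, definite visit, and only Visit 4 fits it. On that reading the close watch is the Day 0 watch and agrees with Table 2. This reading is open. A reader might infer that the protocol contradicts itself, but the text does not establish that. The general heading favours a duty after every administration, while the named end point favours Day 0.

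Lighter follow-up after a second dose is also defensible. The staggering is justified by the lack of previous human experience, and before re-dosing the same subject has a Week 4 skin examination, imaging, wound assessment and blood tests. The protocol also tries to limit travel (section 7.1.3). This stands as a possible rationale, though it is not given as one, and it does not tell a site when the watch ends after Week 4.

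A reader might also infer that wound events after the second dose will go unrecorded. The documents do not support that. The diary runs between visits, nursing support is promised where needed, the must-record sentence of 13.2.1 and the blistering note in 13.1.1 have no dose limit, step 15 of Appendix A covers immediate change in wound size at any administration, and serious events must be reported within 1 working day. However, a diary depends on the subject noticing and writing. The extended stay follows an event already seen. Hotel checks and unscheduled visits are discretionary.

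Finally, little follows formally from a missed non-serious event. Non-serious blistering and border expansion are not, as such, among the suspension triggers in section 11.1.1, and the AE tables are not specified by dose. That limits the weight of the point, but scheduled follow-up still matters where safety is the primary objective.

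**Conclusion.** The point holds as a cheap improvement. After a Week 4 dose to target wounds, the plan requires same-day imaging and AE assessment and then schedules no visit or contact for 56 days (47 to 65 with windows). After Day 0 there is a scheduled skin examination with imaging at 2 days (1 to 3). At most 12 second wound administrations are affected (13 with the optional subject).

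The gap is in scheduled looking, not in recording. Two assumptions underlie it: that wounds are in fact re-dosed at Week 4, and that the near-site stay and daily contact in section 7.3.2 apply to Visit 3 only, as their placement and Table 2, footnote 4, indicate. A reader might infer that a regime of daily wound checks is dropped after the second dose. The documents do not support that, because the period of daily contact is described as monitoring for autoimmune reactions. Nor do they show whether the lighter follow-up was chosen or overlooked.

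**What to change.** In section 7.3.4 and a Table 2 footnote, add one telephone contact 2 days (±1 day) after any Visit 5 administration to target wounds. Use the existing telephone-consult format of Visits 7 and 9 (AEs and concomitant medications), open with the non-leading question of section 13.1.1, and review the AE diary. Arrange an unscheduled visit under section 7.4 if a wound change is reported. An in-person look may replace the call if the subject is still at or near the site.

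Reword the first sentence of 13.2.1 to name the end of the watch after each dose: Visit 4 after the Day 0 dose, and the 2-day contact after a Week 4 wound dose. Leave the must-record sentence unchanged.

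The call should not include directed questions about blisters or wound borders. They would conflict with the non-leading rule in 13.1.1 and make ascertainment uneven between doses. Photographs taken by subjects are also best left out: wound images in this protocol come from the Canfield system (section 9.3), so they would be a new procedure.

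The cost is at most 12 to 13 calls and a protocol amendment with the IRB step in section 16.1. The planned analyses do not change. The main limitation is that a call is less sensitive than the Visit 4 examination and imaging, and mainly prompts what the diary should already capture.

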#### 13.2.2 SAE Reporting Procedures

All serious adverse events must be reported to Fibrocell or designee within 1 working day of the earlier of discovery or notification of the event throughout the duration of the study. Initial serious adverse event information and all amendments or additions must be recorded on a Serious Adverse Event Report Form and faxed or emailed to Fibrocell or designee.

CONFIDENTIAL Page 58 of 75

Final Version 8.0, 29 Oct 2019

## 14 Statistical Considerations

The objectives of this protocol are outlined in Section 2.2 (Objectives).

Treatment visits in this study will include Visits 3 through 10, and unscheduled visits. For efficacy evaluation, the end-of-treatment (or treatment endpoint) will also be defined as a post-treatment assessment time point for efficacy evaluations in order to handle the issue of missing data that is caused by incomplete data collection or early terminations.

## 14.1 Number of Subjects

A formal sample size calculation was not performed for this study. The sample size is based on what was considered an adequate number of subjects for a pilot study to obtain sufficient information on the safety and effectiveness of FCX-007.

#### 14.2 General considerations

Data will be summarized by treatment regimen and, when applicable, by study visit. Descriptive statistics (number and percentage for categorical data, mean, median, range, standard deviation and N for continuous data) will be presented for each evaluable parameter for change from baseline as well as the value at each timepoint. For discrete variables, descriptive analyses will be based on numbers of subjects (or wounds) and related percentages.

All listings, summaries, figures, and statistical analyses will be generated using SAS version 9.1 or other validated software. When applicable, statistical comparisons between treatments will account for correlated and/or paired data since the data are comprised of multiple wounds on the same individual. Statistical analyses will be exploratory and performed using 2-sided tests at a Type I error rate of 0.05.

## 14.3 Data Management

Pre-designed CRFs will be used to collect information for safety and proof of mechanism analyses. A clinical database will be managed by a sponsor's representative for this study. The database will be constructed based on the CRF data entry plus laboratory data information. Data queries will be generated and resolved. In addition, range checks of the CRF fields, plausibility and consistency checks across CRF pages will be performed to assess consistency, accuracy and completeness of the data collected and entered into the CRF. Standard SAS datasets will be generated and provided for analysis.

